5.2 Randomisation, blinding and treatment allocation

There is no randomisation, blinding or treatment allocation, because no investigational product is being administered in this study.

5.3 Study procedures

1. Inclusion Visit (August/September)

At the inclusion visit, after eligibility has been confirmed and fully informed consent completed, the following procedures will take place:

- A baseline questionnaire about, but not limited to, demographic data, medical history, risk factors for RSV disease and quality of life will be completed.
- A blood sample (60 ml) and a nasopharyngeal sample will be collected.
- 2. Throughout the RSV season (October 1st to May 1st, or longer if RSV is still circulating based on national viral surveillance programs):

Participants will be asked about respiratory symptoms during the RSV winter season by weekly contact by telephone (verbally or text message), email, telephone app or online questionnaire. If they experience an ARTI, participants are instructed to contact the study team. Two nasopharyngeal and one oropharyngeal sample will be collected by home visits (or in the doctor's office when preferred by participant) within 3 days after contact with the study team. One nasopharyngeal sample will be used for direct RSV RT-PCR testing. The other samples will be stored at -80°C. If RSV is positive a blood sample will be drawn (60 ml) and a nasopharyngeal sample will be collected and stored at -80°C. In addition, in case of a RSV ARTI, 1-2 weeks after onset of symptoms another blood sample (30ml) and nasopharyngeal sample will be collected. During the episode of respiratory disease, participants are asked to complete a diary on respiratory symptoms and HRQoL. At the end of the episode, participants are asked to complete a questionnaire on medical resource use, interruption of daily activities and HRQoL. If participants have been admitted to the hospital, a questionnaire about the reason for hospitalization, diagnosis and treatment will be completed by the study team using medical data from the admitted hospital.

- 3. At the end of the RSV Season (May/June)
 - A blood sample (60 ml) and a nasopharyngeal sample will be collected.
- 4. Approximately one year after inclusion (+/- 2 months).
 - A questionnaire about changes in living conditions, health status and quality of life will be completed.

 Table 2. Overview of sampling of older adults study.

Moment of	Sample	Volume	Analysis (minimum
sampling		00 1	amount)
At beginning of RSV	Serum (venous)	20 ml	RSV serology (350-400 μl)
season (Oct.)			Proteome (100 µl)*
	Paxgene (venous)	10 ml	Transcriptome (200 µI)*
	Whole blood	30 ml	DNA/GWAS (200 µl)
	(venous)		Epigenetics*
			Cellular immunology#
	Nasopharyngeal	n/a	Airway microbiome
	swab		Airway transcriptome*
ARTI	Nasopharyngeal	n/a	RSV RT-PCR (qualitative)
	swab (2x) and		Multiplex RT-PCR
	oropharyngeal swab		respiratory viruses
			(quantitative) (pending
			funding)
			(RSV viral (deep)
			sequence analysis)
RSV ARTI	Serum (venous)	20 ml	RSV serology (350-400 µl)
			Proteome (100 µl)*
	Paxgene (venous)	10 ml	Transcriptome (200 µI)*
	Whole blood	30 ml	Epigenetics*
	(venous)		Cellular immunology#
	Nasopharyngeal	n/a	Airway microbiome
	swab		Airway transcriptome*
1-2 weeks after RSV	Nasopharyngeal	n/a	Airway microbiome*
ARTI	swab	11/4	All way microbiome
74(11	Whole blood	30 ml	Cellular immunology#
	(venous)	00 1111	Condidi mimanology
At end of RSV	Serum (venous)	20 ml	RSV serology (350-400 µl)
season (May)			Proteome (100 µl)*
	Paxgene (venous)	10 ml	Transcriptome*
	Whole blood	30 ml	Epigenetics*
	(venous)		
	Nasopharyngeal		Airway microbiome
	swab		Airway transcriptome*

^{*} and additional RSV related biomarkers

[#]in subset of subjects

Handling and storage of samples

All samples will be stored at the site where they are collected (medical center or local laboratory):

- Blood samples will be collected in appropriate tubes as described in table 2 and will be stored at -80°C for later analysis.
- Nasopharyngeal swab: a nasopharyngeal swab will be collected and aliquoted directly in 3-4 samples of 200 microliter. All aliquots will be stored at -80°C for later analysis
- Oropharyngeal swab: an oropharyngeal swab will be collected and stored at -80°C for later analysis.

5.4 Withdrawal of individual participants

Participants can withdraw from the study at any time without having to provide a reason if they wish to do so and without any consequences for their health care. The investigator can also decide to withdraw a subject from the study if they meet the pre-defined exclusion criteria (see section 4.3).

Withdrawal of consent: If consent is withdrawn, the participant will not have any further study procedures or study observations. All previously collected samples and data will be retained and used as planned, unless consent is specifically withdrawn for this.

Lost to follow-up: Participants will be considered lost-to-follow-up only if no contact has been established by the time the study is completed such that there is insufficient information to determine the subject's RSV status at approximately 1 year.

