4.3 Exclusion criteria for enrolment

The following criteria should be checked at the time of study entry. If ANY exclusion criterion applies, the subject must not be included in the study:

- Current alcohol or drug abuse or history of unsuccessfully treated alcohol or drug abuse within the past year
- Unable to perform the study procedures
- Dementia
- Life expectancy less than 1 year
- Any known or suspected immunosuppressive condition, acquired or congenital, as determined by history and/or physical examination (a more detailed description/list can be found in appendix 3).
- Chronic administration (defined as more than 14 continuous days) of immunosuppressants or other immune-modifying drugs within 6 months prior to study participation. The use of topical, inhaled, and nasal glucocorticoids will be permitted (a more detailed description/list can be found in appendix 3).
- Previous participation in this study or in a RSV interventional trial (vaccine, antivirals).
- Planned leave/holiday during the winter season of more than 1 month in total.

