5.1.2 Secondary study parameters/endpoints

- The incidence rate of all-cause MA-ARTI or events leading to worsening of cardiorespiratory status. The incidence rate will also be summarized separately for outpatient events and for both inpatient and outpatient events combined through the RSV season of follow up. Subgroup analyses will summarize these endpoints by RSV season.
- 2. Mortality through the RSV season of follow up for RSV-associated deaths and all cause deaths.
- 3. Health care costs and resource use for RSV-associated and all-cause MA-ARTI (inpatient or outpatient) or events leading to worsening cardiorespiratory status with regard to hospital duration, incidence and duration of intensive care unit stay, supplemental oxygen use, antibiotic and antiviral use and number of outpatient visits (e.g., ER visit, physician office/outpatient visits) and HRQoL.
- The incidence rate of RSV-associated secondary bacterial pneumonia events (defined as pneumonia within 21 days after RSV infection) and associated antibiotic use will be summarized.
- 5. Change in frailty over the course of study.
- 6. Sample collection for biomarker analysis to investigate possible biomarkers which are predictive of severe or complicated RSV disease in older adults. With these

clinical samples a biobank will be established for identifying potential biomarkers of RSV disease severity for further validation.

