5.5 Replacement of individual participants after withdrawal

After withdrawal of an individual participant he or she will be replaced depending on the moment of withdrawal.

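### Section 5.4 lets the investigator withdraw enrolled participants on the Section 4.3 exclusion criteria without limiting this to criteria present at entry, which could bias hospitalization, mortality and frailty results downward

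*Protocol*

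**What the plan says.** Protocol Section 5.4 gives the investigator a discretionary power: "The investigator can also decide to withdraw a subject from the study if they meet the pre-defined exclusion criteria (see section 4.3". It sets no time limit and does not require that the criterion was already present when the participant was enrolled.

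Section 4.3, to which it refers, is about enrolment: "The following criteria should be checked at the time of study entry". Its list includes "Life expectancy less than 1 year", "Any known or suspected immunosuppressive condition, acquired or congenital, as determined by history and/or physical examination", "Unable to perform the study procedures" and dementia. Appendix 3 adds examples of immunosuppression-related exclusions, among them active haematological malignancy and end-stage renal or hepatic failure.

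On data handling, Section 5.4 says: "All previously collected samples and data will be retained and used as planned, unless consent is specifically withdrawn for this". That sentence stands under withdrawal of consent; nothing equivalent is stated for withdrawal by the investigator. Section 5.5 adds: "After withdrawal of an individual participant he or she will be replaced depending on the moment of withdrawal".

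The outcomes concerned are RSV-related hospitalization (a primary endpoint in the Summary and part of the primary analysis in Section 4.4) and two secondary endpoints in Section 5.1.2: "Mortality through the RSV season of follow up for RSV-associated deaths and all cause deaths", and change in frailty.

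**The concern.** A list written to decide who enters the cohort is reused, without qualification, to decide who may be taken out of it. In adults aged 60 and over, about half of them at least 75, several of the listed states can begin during a year of follow-up. People who reach them can reasonably be expected to have an above-average risk of admission and death. If they leave observation at that point, the loss is related to the outcome and is not random.

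The study gives no investigational product (Section 5.2), so no product-safety reason calls for ending observation. The purpose is to measure burden of disease, and these people carry part of that burden. Events that occur after they leave would not be collected, and no later analysis could recover them.

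**Working it through.** **Step 1. Set the sections side by side.**

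| Question | Section 4.3 | Section 5.4 |
|---|---|---|
| When do the criteria apply? | At study entry | Not stated |
| Consequence | Not enrolled | Investigator may withdraw |
| Limited to errors at entry? | Follows from the timing | Not stated |
| Outcome or vital status afterwards? | Not applicable | Not provided for |

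**Step 2. Which criteria can first be met during follow-up?**
- Can arise later: short life expectancy, dementia, inability to carry out the procedures, an immunosuppressive condition.
- Tied to entry by their wording or nature: earlier participation in this study or an RSV interventional trial, planned winter absence, and chronic immunosuppressant use, which is counted over the six months before participation.

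So the open wording of 5.4 has practical effect for four criteria.

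**Step 3. Illustrate the size.** The protocol states no figure on this point, so there is none to reproduce. All inputs below are assumptions:
- w, the share of the cohort withdrawn in this way: 1% to 5%.
- s, the fraction of follow-up lost: 0.5 (withdrawal halfway).
- RR, the event rate of these people after that point relative to everyone else: 2 to 5. Before that point they are given the base rate.

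With the base rate set to 1:

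True relative rate = (1 − w) + w × [(1 − s) + s × RR]

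If person-time is censored at withdrawal, the observed relative rate is 1, and the relative bias is 1/True − 1.

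| w | RR | True relative rate | Relative bias |
|---|---|---|---|
| 1% | 2 | 0.99 + 0.01 × 1.5 = 1.005 | −0.5% |
| 1% | 5 | 0.99 + 0.01 × 3.0 = 1.020 | −2.0% |
| 3% | 2 | 0.97 + 0.03 × 1.5 = 1.015 | −1.5% |
| 3% | 5 | 0.97 + 0.03 × 3.0 = 1.060 | −5.7% |
| 5% | 2 | 0.95 + 0.05 × 1.5 = 1.025 | −2.4% |
| 5% | 5 | 0.95 + 0.05 × 3.0 = 1.100 | −9.1% |

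With RR = 1 the bias is zero; it is downward whenever RR exceeds 1.

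**Step 4. Check the denominator.** Section 4.4 describes ratios of cases to numbers of people. If everyone enrolled stays in the denominator, the observed relative rate is 1 − 0.5w. The bias is then 0.995/1.005 − 1 = −1.0% at w = 1%, RR 2, and 0.975/1.100 − 1 = −11.4% at w = 5%, RR 5. The direction is the same and the size slightly larger.

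This model covers event rates. For change in frailty only the direction can be argued: people withdrawn because they can no longer carry out the procedures, or because of dementia, would miss the one-year questionnaire, so worsening would be understated.

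**The case against.** The strongest reply is that 5.4 was meant only for people found after enrolment to have been ineligible. It points back to a section headed as enrolment criteria, some of those criteria make sense only at entry, and the wording permits withdrawal without requiring it. This reading is plausible and it stands: the protocol does not show that anyone would be withdrawn for a new condition. But the text does not say so, and if that is the intent, stating it costs nothing.

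Three stronger readings are tempting, and the documents do not support them:
- A reader might infer that a steroid course given for an in-season exacerbation would trigger withdrawal. Section 4.3 and Appendix 3 tie that criterion to the six months before participation.
- A reader might infer that becoming frail is itself a ground. Frailty is not an exclusion criterion; only dementia or inability to carry out the procedures comes near it.
- A reader might infer that replacements would be in better health. Section 5.5 says only that replacement depends on timing, and recruitment runs from May to October, which also fits replacing early withdrawals.

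It can also be said that the possible bias is small beside sampling error. For 24 cases in 800 (the planned 3%), the exact 95% interval is 1.93% to 4.43%. That is a fair statement of scale for medically attended RSV. It is not a defence, because the interval does not reflect this bias. Hospitalizations are also a subset of about 30 expected medically attended cases (3% of 1,000), so single missed admissions count.

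Two further points have force. A person who cannot be swabbed cannot become an RT-PCR-confirmed case, so keeping all of that person's time in the denominator would itself lower the incidence; the fix has to allow for this. And censoring rules are often left to a statistical analysis plan. What is at issue here, however, is whether follow-up continues at all, and that is a conduct rule for the protocol.

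**Conclusion.** The point holds as a defect of wording with a possible bias, not as a demonstrated bias. Sections 5.4 and 4.3 do not agree on when the exclusion criteria apply. The open reading allows higher-risk participants to leave observation with no provision for collecting their outcomes.

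If the rule is used that way, RSV hospitalization and mortality would be biased downward and worsening of frailty understated, provided those withdrawn carry the higher risk. The size cannot be derived from the protocol. The illustration gives about −0.5% to −9% in relative terms with person-time censored, and rests on assumed values for the share withdrawn, the rate ratio and withdrawal at the midpoint. A reader might want a larger headline figure, for mortality especially, but the protocol gives no number of deaths, rate of terminal illness or withdrawal rate to support one.

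This is a cheap improvement.

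**What to change.** 1. Reword 5.4 to agree with 4.3: the investigator may withdraw a participant on these grounds only when an exclusion criterion is found to have been present at enrolment.
2. State that a participant who first meets a criterion later stays under follow-up for outcomes and vital status, with fewer procedures where needed, unless consent is withdrawn.
3. State that data from these participants are retained. For RT-PCR-confirmed endpoints, count person-time only while symptom surveillance and swabbing remain possible; hospitalization from any source and vital status continue to be recorded.
4. Align 5.5, so that replacement is not triggered by a condition that arises during follow-up, and say what the moment of withdrawal means for replacement.

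The cost is a few sentences in 5.4 and 5.5. The downside is that a few participants are followed with fewer samples.

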4.4 Sample size calculation

For the primary analysis the ratio between cases of RSV-related hospitalizations and number of older adults in the total population will be calculated. In addition, the ratio between the cases of MA-RSV infection and the number of older adults undergoing active surveillance will be calculated.

To estimate the incidence of MA-RSV infection and RSV-related hospitalization at an older age, a prospective cohort of approximately 1,000 older adults ≥60 is followed for 1 year. For sample size calculations a statistic expert of the Julius Support Center was consulted. Assuming a yearly MA-RSV incidence of 3,0% based on literature^{5,9}, a sample size of 800 will produce a two-sided >95% confidence interval with a symmetric half width of 0.01 Version number: 3, July 29th 2019

(Confidence interval formula: Exact, Clopper-Pearson). Accounting for a 10% loss to follow up, approximately 1000 elderly will be included in the cohort.

Patient population	Sites	Outcome	Persons	RSV seasons	Expected Incidence per year (%)	95% Confidence Interval Half-Width (%)
Older Adults (≥ 60 years)	NL, UK, BE	Incidence rate of MA-RSV	1,000	1	3,0 ^{5,9}	1,9 – 5,0

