Acute respiratory tract infection (ARTI): symptoms of an upper and/or lower respiratory tract infection, such as runny or blocked nose, coughing, fast breathing, chest indrawing, shortness of breath, low oxygen saturation.

Cohort study: A form of epidemiological study where subjects in a study population are classified according to their exposure status/disease and followed over time (prospective/retrospective) to ascertain the outcome(s).

Epidemiological study: An observational or interventional study without administration of medicinal product(s) as described in a research protocol.

Evaluable: Meeting all eligibility criteria, complying with the procedures defined in the protocol, and, therefore, included in the According-To-Protocol (ATP) analysis (see Section 9.3 for details on criteria for evaluability).

Health Burden: Burden of the disease imposed on the study population in terms of incidence of the disease and associated healthcare utilization in any healthcare setting.

Healthcare settings (Healthcare Utilization): Primary, secondary and tertiary care settings such as self-care with over-the-counter [OTC] drugs, general practitioner (GP) visits, emergency room (ER) visits, hospital visits, etc.

Interventional Human Subject Research:

Studies in which participants are administered medical care, medicinal products and/or medical/scientific procedures as described in a research protocol.

Lost-to-Follow-up is defined as no contact by the subject's parent(s)/LAR(s) over the period of 3 planned contacts and/or 2 months and after a final attempt has been made by mail. Once this has been reached, the subject is censored at the time of last contact.

Sponsor: The sponsor is the party that commissions the organisation or performance of the research, for example a pharmaceutical company, academic hospital, scientific organisation or investigator. A party that provides funding for a study but does not commission it is not regarded as the sponsor, but referred to as a subsidising party.

Prospective study: A study in which the subjects/cases are identified and then followed forward in time in order to address one or more study objectives.

Research protocol: A document that describes the objective(s), design, methodology, statistical considerations, and organization of a study. The protocol usually also gives the background and rationale for the study, but these could be provided in other protocol referenced documents.

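### Section 5.4 and Appendix 2 define loss to follow-up incompatibly, and the head-count proportions in Section 4.4 have no place for censoring, so time at risk for the primary incidence is undefined and incidence may be understated

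*Protocol*

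**What the plan says.** Section 5.4 sets the rule for loss: "Participants will be considered lost-to-follow-up only if no contact has been established by the time the study is completed", continuing "such that there is insufficient information to determine the subject's RSV status at approximately 1 year".

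Appendix 2 (Glossary of Terms) sets another. It begins "Lost-to-Follow-up is defined as no contact by the subject's parent(s)/LAR(s) over the period of 3 planned contacts and/or 2 months", adds a final attempt by mail, and then says "Once this has been reached, the subject is censored at the time of last contact".

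The endpoint in Table 1 and Section 5.1.1 is an incidence rate of RT-PCR confirmed events. Section 4.4 describes the calculation as ratios. For medically attended RSV, "the ratio between the cases of MA-RSV infection and the number of older adults undergoing active surveillance will be calculated". For hospitalization, "the ratio between cases of RSV-related hospitalizations and number of older adults in the total population will be calculated". The interval named there is Clopper-Pearson. Section 4.4 also allows for 10% loss to follow-up.

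On replacement, Section 5.5 says only that after withdrawal "he or she will be replaced depending on the moment of withdrawal". Section 7 promises descriptive statistics for the incidence rates and gives no rule for time at risk.

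**The concern.** The two definitions can classify the same person differently. Sections 3 and 5.3 plan weekly contact in the season, so Appendix 2 can be met within weeks. Section 5.4 looks only at the end of the study. A participant who stops answering in November and returns the one-year questionnaire can be lost and censored under Appendix 2, yet not lost under Section 5.4.

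The Section 5.4 test also does not fit the endpoint. An RT-PCR confirmed case needs a swab taken during the episode, which Section 5.3 schedules within three days of the participant contacting the team. The one-year contact is a questionnaire and cannot establish a past RT-PCR result.

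Appendix 2 is no clear tie-breaker. Its and/or leaves two thresholds open, and it speaks of parents or LARs in a cohort aged 60 and over.

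At stake are the denominator of the primary objective and the meaning of the 10% loss allowance, which depends on which definition of loss applies.

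**Working it through.** **Inputs from the protocol.** Expected yearly incidence of medically attended RSV 3.0%, cohort about 1,000, planned loss 10% (Section 4.4). Season October 1st to May 1st, weekly contact (Section 3).

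**Assumed inputs; the protocol gives none of these.**
- L: share of participants silent for part of the season but reached later.
- u: mean fraction of the season they go unobserved.
- c: share of their cases in that time that are still captured.
- Risk is constant over the season, and silence is unrelated to risk.

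**Step 1: how far apart the rules are.** October 1st to May 1st is 212 days, about 30 weeks. Three weekly contacts are 21/212 = 10% of the season. Two months are about 61/212 = 29%. Section 5.4 has no in-season limit, so up to 100% of the season can pass in silence.

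**Step 2: the plan's precision, for scale.** The Clopper-Pearson interval for 30/1,000 is 2.03% to 4.26%, a half-width of 1.11 points. The table in Section 4.4 prints 1.9 to 5.0, which this does not reproduce. That is a separate matter and does not affect this point.

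**Step 3: effect of keeping silent participants as full-season non-cases.** Reported incidence = 3.0% × [1 − L × u × (1 − c)].

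| L | u | c | Reported | Relative shift |
|---|---|---|---|---|
| 5% | 0.50 | 0 | 2.93% | −2.5% |
| 10% | 0.25 | 0 | 2.93% | −2.5% |
| 10% | 0.50 | 0 | 2.85% | −5% |
| 10% | 1.00 | 0 | 2.70% | −10% |
| 20% | 0.50 | 0 | 2.70% | −10% |
| 10% | 0.50 | 0.5 | 2.93% | −2.5% |
| any | any | 1 | 3.00% | 0 |

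**Step 4: what censoring does.** Take N = 1,000, L = 10%, u = 0.50, c = 0. Cases observed: 30 × 0.95 = 28.5. Person-seasons observed: 1,000 × 0.95 = 950. Then 28.5/950 = 3.00%, against 28.5/1,000 = 2.85% by head count.

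**Step 5: a trap in the correction.** Suppose silent participants still call in every infection (c = 1), and each call counts as an event while the silent weeks before it are removed. Then 30/950 = 3.16%, an overstatement of 5%. The head count is unbiased in that case. The rule for re-entry therefore matters as much as the rule for loss.

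**The case against.** A reader might infer that Section 5.4 itself puts unsurveilled weeks into the primary denominator as RSV-free, and so always biases incidence downward. The protocol does not support that.

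- Section 5.4 defines a status. It sets no denominator, and its qualifier about insufficient information means that not every late contact counts as full follow-up.
- The medically attended RSV ratio is limited to adults under active surveillance, which can be read to exclude silent participants. The hospitalization ratio carries no such limit.
- Cases can be found without the weekly contact. Participants are told to contact the team when they have an infection, and admissions are documented from hospital data. Paired serology is there for infections that surveillance misses, and the one-year questionnaire asks about past respiratory disease. Serology and questionnaires do not give RT-PCR confirmation, but self-reported episodes can be swabbed.
- Nothing says that withdrawn participants or replacements get full weight. Recruitment runs to October, but inclusion visits are set for August/September, so late entry is not established either.
- Cumulative incidence over one season is a legitimate measure, and a SAP may define person-time.
- Appendix 2 looks like text carried over from a paediatric template.

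These objections remove the claim of certain bias. They do not remove the contradiction: a SAP would still inherit two protocol definitions, one of which requires a censoring that the Section 4.4 ratios cannot apply.

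**Conclusion.** The point holds as a contradiction with a conditional effect. The two rules cannot both be followed. Understatement follows only if silent participants are retained as full-season non-cases and their episodes go uncaptured.

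With L set at the planned 10% loss and no capture, the shift is 0.08 to 0.30 points on 3.0% as the unobserved fraction runs from a quarter to the whole season. That is well inside the half-width of about 1.1 points. It is systematic, however, and a larger cohort would not reduce it. The hospitalization ratio is the most exposed because of its unrestricted denominator, although hospital records may recover some admissions. Differences by country or season are possible, but the protocol gives nothing from which to size them.

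This should be fixed. The contradiction itself is certain; the size of any bias rests entirely on assumed shares.

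**What to change.** 1. Keep one definition of loss, based on missed in-season surveillance contacts, with time censored at the last completed contact. State a single threshold, use it in Section 5.4 and Appendix 2, and delete the reference to parents or LARs.
2. Estimate each primary incidence as events per person-time under active surveillance in the RSV season, with an exact Poisson interval. Replacements contribute from their own inclusion date. Keep the Clopper-Pearson proportion as supportive.
3. After a gap, restart person-time only at a contact not prompted by a reported respiratory infection. Alternatively, show the estimate with and without the episodes that triggered re-entry.

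The cost is mainly wording, since weekly contacts should already yield the dates. There is slightly less person-time: with the 5% reduction in Step 4, the interval is about 1/√0.95 = 1.03 times as wide as with full observation. A few self-reported cases drop out of the main rate if re-entry is restricted.
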